## 9 ATTACHMENTS

Study Code: CSOM230B2410

**9.1 PROTOCOL DEVIATION LIST**

Protocol Deviation ID	Description used to Report PDs to HA/IRBs
I01	Written informed consent or equivalent document not signed
I02	Patient aged less than 18 years
I03	Patients with no confirmed diagnosis of Cushing's disease
I04	Patients with diagnosis of Cushing's disease for whom surgery has not failed
I05	Patients with Cushing's syndrome for whom surgery is an option
I06	Patient started pasireotide s.c. after the first study visit
E01	Patient with ectopic ACTH-dependent Cushing's syndrome
E02	Patient with adrenal Cushing's syndrome
E03	Patient with Pseudo Cushing's syndrome
G01	Informed consent not appropriately obtained
G02	SAE not reported within 24 hours of awareness

Study Code: CSOM230B2410

## 9.2 AESI LIST

Category	Adverse Event Term
AESI Bradycardia related AEs	Atrial conduction time prolongation (PT) Atrioventricular block (PT) Atrioventricular block complete (PT) Atrioventricular block second degree (PT) Atrioventricular dissociation (PT) Bradycardia (PT) Central bradycardia (PT) Conduction disorder (PT) Defect conduction intraventricular (PT) Electrocardiogram PQ interval prolonged (PT) Electrocardiogram PR prolongation (PT) Electrocardiogram QRS complex prolonged (PT) Electrocardiogram QT prolonged (PT) Long QT syndrome (PT) Paroxysmal atrioventricular block (PT) Sinoatrial block (PT) Sinus bradycardia (PT)
AESI Coagulation related AEs	Blood fibrinogen decreased (PT) Blood thrombin decreased (PT) Blood thromboplastin abnormal (PT) Blood thromboplastin decreased (PT) Coagulation factor IX level decreased (PT) Coagulation factor V level decreased (PT) Coagulation factor VII level decreased (PT) Coagulation factor X level decreased (PT) Coagulation factor decreased (PT) Hypofibrinogenaemia (PT) International normalised ratio abnormal (PT) Prothrombin level decreased (PT) Prothrombin time prolonged (PT) Prothrombin time ratio decreased (PT) Thrombin time prolonged (PT)
AESI Gallbladder and biliary related AEs	Bile duct necrosis (PT) Bile duct obstruction (PT) Bile duct stenosis (PT) Bile duct stone (PT) Bile output abnormal (PT) Bile output decreased (PT)

Study Code: CSOM230B2410

Category	Adverse Event Term
	Bile output increased (PT)
	Biliary cirrhosis (PT)
	Biliary colic (PT)
	Biliary dilatation (PT)
	Biliary dyskinesia (PT)
	Biliary dyspepsia (PT)
	Biliary fibrosis (PT)
	Biliary fistula (PT)
	Biliary ischaemia (PT)
	Biliary tract disorder (PT)
	Bilirubin conjugated abnormal (PT)
	Bilirubin conjugated increased (PT)
	Bilirubin excretion disorder (PT)
	Bilirubin urine present (PT)
	Bilirubinuria (PT)
	Blood alkaline phosphatase abnormal (PT)
	Blood alkaline phosphatase increased (PT)
	Blood bilirubin abnormal (PT)
	Blood bilirubin increased (PT)
	Blood bilirubin unconjugated increased (PT)
	Cholangiogram abnormal (PT)
	Cholecystectomy (PT)
	Cholecystitis (PT)
	Cholecystitis acute (PT)
	Cholecystitis chronic (PT)
	Cholecystogram intravenous abnormal (PT)
	Cholecystogram oral abnormal (PT)
	Cholelithiasis (PT)
	Cholelithiasis migration (PT)
	Cholelithiasis obstructive (PT)
	Cholestasis (PT)
	Deficiency of bile secretion (PT)
	Endoscopy biliary tract abnormal (PT)
	Gallbladder disorder (PT)
	Gallbladder enlargement (PT)
	Gallbladder fibrosis (PT)
	Gallbladder fistula (PT)
	Gallbladder hypofunction (PT)
	Gallbladder necrosis (PT)

Study Code: CSOM230B2410

Category	Adverse Event Term
	Gallbladder obstruction (PT)
	Gallbladder oedema (PT)
	Gallbladder operation (PT)
	Gallbladder palpable (PT)
	Haemobilia (PT)
	Hepatitis cholestatic (PT)
	Hepatobiliary disease (PT)
	Hyperbilirubinaemia (PT)
	Jaundice (PT)
	Jaundice cholestatic (PT)
	Jaundice extrahepatic obstructive (PT)
	Obstructive pancreatitis (PT)
	Perforation bile duct (PT)
	Pseudocholelithiasis (PT)
	Ultrasound biliary tract abnormal (PT)
	Urine bilirubin increased (PT)
	X-ray hepatobiliary abnormal (PT)
AESI Growth hormone deficiency related AEs	Blood growth hormone decreased (PT)
	Insulin-like growth factor decreased (PT)
AESI Hyperglycemia-related AEs	Blood glucose increased (PT)
	Blood insulin decreased (PT)
	Diabetes mellitus (PT)
	Diabetes mellitus inadequate control (PT)
	Diabetes with hyperosmolarity (PT)
	Diabetic coma (PT)
	Diabetic hyperglycaemic coma (PT)
	Diabetic hyperosmolar coma (PT)
	Diabetic ketoacidosis (PT)
	Diabetic ketoacidotic hyperglycaemic coma (PT)
	Diabetic ketosis (PT)
	Fructosamine increased (PT)
	Glucose tolerance decreased (PT)
	Glucose tolerance impaired (PT)
	Glucose tolerance test abnormal (PT)
	Glucose urine (PT)
	Glycosuria (PT)
	Glycosylated haemoglobin increased (PT)
	Hyperglycaemia (PT)
	Hyperglycaemic hyperosmolar nonketotic syndrome (PT)

Study Code: CSOM230B2410

Category	Adverse Event Term
	Impaired fasting glucose (PT)
	Impaired insulin secretion (PT)
	Increased insulin requirement (PT)
	Insulin-requiring type 2 diabetes mellitus (PT)
	Ketoacidosis (PT)
	Ketonuria (PT)
	Ketosis (PT)
	Ketosis-prone diabetes mellitus (PT)
	Monogenic diabetes (PT)
	Type 1 diabetes mellitus (PT)
	Type 2 diabetes mellitus (PT)
AESI Hypocortisolism related AEs	Adrenal insufficiency (PT)
	Adrenal suppression (PT)
	Adrenocortical insufficiency acute (PT)
	Cortisol decreased (PT)
	Cortisol deficiency (PT)
	Cortisol free urine decreased (PT)
	Glucocorticoid deficiency (PT)
	Glucocorticoids decreased (PT)
	Secondary adrenocortical insufficiency (PT)
	Steroid withdrawal syndrome (PT)
AESI Hypotension related AEs	Blood pressure ambulatory decreased (PT)
	Blood pressure decreased (PT)
	Blood pressure diastolic decreased (PT)
	Blood pressure immeasurable (PT)
	Blood pressure orthostatic abnormal (PT)
	Blood pressure orthostatic decreased (PT)
	Blood pressure systolic decreased (PT)
	Hypotension (PT)
	Mean arterial pressure decreased (PT)
AESI Hypothyroidism related AEs	Blood thyroid stimulating hormone decreased (PT)
	Hypothyroidism (PT)
	Myxoedema (PT)
	Myxoedema coma (PT)
	Secondary hypothyroidism (PT)
	Thyroid dermatopathy (PT)
	Thyroid stimulating hormone deficiency (PT)
	Thyroxine free decreased (PT)
	Tri-iodothyronine decreased (PT)

Study Code: CSOM230B2410

Category	Adverse Event Term
	Tri-iodothyronine free decreased (PT)
AESI Injection site reaction related AEs	Administration site abscess (PT) Immediate post-injection reaction (PT) Injection site atrophy (PT) Injection site bruising (PT) Injection site discolouration (PT) Injection site discomfort (PT) Injection site erosion (PT) Injection site erythema (PT) Injection site exfoliation (PT) Injection site granuloma (PT) Injection site haematoma (PT) Injection site haemorrhage (PT) Injection site hypersensitivity (PT) Injection site inflammation (PT) Injection site irritation (PT) Injection site necrosis (PT) Injection site nodule (PT) Injection site oedema (PT) Injection site pain (PT) Injection site pruritus (PT) Injection site rash (PT) Injection site reaction (PT) Injection site swelling (PT) Injection site urticaria (PT)
AESI Liver safety related AEs	Alanine aminotransferase abnormal (PT) Alanine aminotransferase increased (PT) Ammonia increased (PT) Aspartate aminotransferase abnormal (PT) Aspartate aminotransferase increased (PT) Blood cholinesterase abnormal (PT) Blood cholinesterase decreased (PT) Computerised tomogram liver abnormal (PT) Gamma-glutamyltransferase abnormal (PT) Gamma-glutamyltransferase increased (PT) Guanase increased (PT) Hepatic enzyme abnormal (PT) Hepatic enzyme decreased (PT) Hepatic enzyme increased (PT)

Study Code: CSOM230B2410

Category	Adverse Event Term
	Hepatic function abnormal (PT) Hepatobiliary scan abnormal (PT) Hyperammonaemia (PT) Hypertransaminasaemia (PT) Liver function test increased (PT) Transaminases abnormal (PT) Transaminases increased (PT) Ultrasound liver abnormal (PT) Urine bilirubin increased (PT)
AESI Low blood cell related AEs	Anaemia (PT) Febrile neutropenia (PT) Haematocrit decreased (PT) Haemoglobin decreased (PT) Leukopenia (PT) Lymphocyte count decreased (PT) Lymphopenia (PT) Neutropenia (PT) Platelet count decreased (PT) Red blood cell count decreased (PT) Thrombocytopenia (PT)
AESI Pancreatitis related AEs	Abdominal compartment syndrome (PT) Blood trypsin increased (PT) Fat necrosis (PT) Hyperlipasaemia (PT) Lipase abnormal (PT) Lipase increased (PT) Pancreatic enzyme abnormality (PT) Pancreatic enzymes abnormal (PT) Pancreatic enzymes increased (PT) Pancreatitis (PT) Pancreatitis acute (PT) Pancreatitis haemorrhagic (PT) Pancreatitis necrotising (PT) Pancreatitis relapsing (PT) Peripancreatic fluid collection (PT)
AESI QT-prolongation-related AEs	Cardiac arrest (PT) Cardiac death (PT) Cardiac fibrillation (PT) Cardio-respiratory arrest (PT)

Study Code: CSOM230B2410

Category	Adverse Event Term
	Electrocardiogram QT interval abnormal (PT)
	Electrocardiogram QT prolonged (PT)
	Electrocardiogram repolarisation abnormality (PT)
	Long QT syndrome (PT)
	Loss of consciousness (PT)
	Sudden cardiac death (PT)
	Sudden death (PT)
	Syncope (PT)
	Torsade de pointes (PT)
	Ventricular arrhythmia (PT)
	Ventricular fibrillation (PT)
	Ventricular flutter (PT)
	Ventricular tachyarrhythmia (PT)
	Ventricular tachycardia (PT)

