⁶ Monitoring of liver function after one, two, four, eight and twelve weeks
⁷ one week after start of treatment, QTcF/QTcB prolongations > 480 msec have to be reported as adverse events
* **Hematology:** WBC, RBC, Hemoglobin, Hematocrit, Platelets, Neutrophils, Lymphocytes, Eosinophils, Basophils, Monocytes
Blood chemistry: γGT, α-amylase, Total bilirubin, Indirect bilirubin, Direct bilirubin, Sodium, Potassium, Magnesium, GH, IGF-1, PT, Plasma ACTH, Triglyceride, Cholesterol, LDL, HDL

Recommended assessments are specified and listed in the local product label.

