3.5.2.8 Laboratory evaluations

Mild transient elevations in aminotransferases are observed commonly in patients treated with pasireotide. Rare cases of concurrent elevations in ALT greater than 3xULN and bilirubin greater than 2xULN have also been observed.

Monitoring of liver function is recommended prior to treatment with pasireotide s.c. and after one, two, four, eight and twelve weeks during treatment. Thereafter liver function should be monitored as clinically indicated.

Patients who develop increased transaminase levels should be monitored with a second liver function evaluation to confirm the finding. If the finding is confirmed, the patient should be followed with frequent liver function monitoring until values return to pre-treatment levels. Therapy with pasireotide s.c. should be discontinued in case the patient develops jaundice or other signs suggestive of clinically significant liver dysfunction, in case of a sustained increase in AST or ALT of 5x ULN or greater, or if ALT elevations greater than 3xULN occur concurrently with bilirubin elevations greater than 2xULN. Following discontinuation of treatment with pasireotide s.c. patients should be monitored until resolution.

As the pharmacological activity of pasireotide s.c. mimics that of somatostatin, inhibition of pituitary hormones other than ACTH cannot be ruled out. Monitoring of pituitary function (e.g. TSH/free T₄, GH/IGF-1) before and periodically during pasireotide s.c. therapy should therefore be considered, as clinically appropriate.

Available data on the following laboratory parameters will be collected in this study:

- AST
- ALT
- Alkaline phosphatase
- γ GT
- α -amylase
- Total bilirubin
- WBC
- RBC
- Hemoglobin
- Hematocrit
- Platelets
- Sodium

- Potassium
- Magnesium
- Fasting Plasma Glucose
- HbA1C
- GH
- IGF-1
- TSH
- Free T4
- PT
- APTT

If total bilirubin concentration is increased above 2.0 times upper limit normal (ULN), total bilirubin is recommended to be differentiated into the direct and indirect reacting bilirubin.

All local laboratories contributing to the study should provide the sponsor with a copy of each laboratory's certification and a tabulation of the normal ranges and standard deviations from control values for each of the parameters being evaluated. These laboratory references should be forwarded to the sponsor prior to study start and updated promptly if any information changes during the course of the study.

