6.5.2 Safety evaluation

For all safety analyses, the safety set will be used. Safety analysis will be stratified by incident or prevalent use of the drug.

Safety and tolerability assessments include AEs, vital signs, blood pressure, heart rate, body temperature, blood glucose (fasting plasma glucose, HemoglobinA1c), hormones (GH, IGF-1, TSH/free T₄), liver enzymes (AST, ALT, alkaline phosphatase, γGT, total bilirubin), hematology, electrolytes, immunological events (e.g., allergic reactions: rash, pruritus, injection site reactions), gallbladder ultrasound and ECGs.

The overall safety observation period will be divided into two mutually exclusive segments:

1. on-treatment period: from day of enrolling into the study to 28 days after last dose of pasireotide s.c.-
2. post-treatment period: starting at day 28+1 after last dose of pasireotide s.c.

Safety data will be largely collected for the on-treatment period.

For continuous safety variables, the change from the last dose of pasireotide s.c. to 3 months after permanent discontinuation of pasireotide s.c. for patients that discontinue pasireotide s.c. prior to completing the 3-year observation period will be summarized.

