#### 8.1.2 Statistical hypothesis, model, and method of analysis

The sample size for this study is not based on statistical considerations. It is anticipated that up to approximately 100 sites in about 35 countries will participate in the study. The study will enroll a minimum of 100 patients up to a maximum of 200 patients. The actual sample size may differ from this planned number.

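### SAP Attachment 9.2 lists alkaline phosphatase, blood bilirubin and jaundice only under gallbladder/biliary and has no amylase, APTT, neutrophil-count or white-cell-count term, so four AESI category counts may be too low

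*SAP*

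**What the plan says.** Protocol 3.5.2.3 names increased liver enzymes, cholelithiasis and haematological abnormalities as separate identified risks, and pancreatitis and coagulation abnormalities as potential risks. Protocol 6.5.2.1 asks for AESI summaries by category according to those risks. SAP 8.4.1 counts patients with at least one event in each grouping. It takes the groupings from Attachment 9.2, in the latest form available before database lock.

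On what belongs to the liver, protocol 6.5.2 lists "liver enzymes (AST, ALT, alkaline phosphatase, γGT, total bilirubin" as one group, and SAP 8.4 repeats that grouping. Protocol 3.5.2.8 links jaundice to the liver: "in case the patient develops jaundice or other signs suggestive of clinically significant liver dysfunction".

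Attachment 9.2 puts "Blood alkaline phosphatase increased (PT", "Blood bilirubin increased (PT" and "Jaundice cholestatic (PT" under gallbladder and biliary. None of the three is in the liver safety list.

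For the pancreas, the blood chemistry footnote to protocol Table 3-1 includes "γGT, α-amylase, Total bilirubin", and neither it nor the list in 3.5.2.8 names lipase. The pancreatitis category holds "Lipase increased (PT" and other enzyme terms, but none for amylase.

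**The concern.** The point concerns the content of categories that exist, not categories that are absent. An AESI category is a fixed list of terms: an event coded to a term outside the list does not count towards that risk, whatever its clinical meaning. If the lists do not match the tests that the protocol collects, the patient count for a named risk can be too low.

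This matters because safety is the study's primary objective. The AESI tables show each risk category by grade and seriousness, and AESIs by relationship, discontinuation, dose adjustment and time of onset. A laboratory abnormality becomes an adverse event only if it is symptomatic, clinically significant or treated (protocol 3.5.2.1), so the events at issue are ones that a site judged worth reporting.

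A rise in aminotransferases together with bilirubin, a combination that protocol 3.5.2.8 mentions, would be divided between two categories.

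**Working it through.** There is no power or sample-size figure to reproduce; the SAP says "The sample size for this study is not based on statistical considerations". The check is a search of five lists in Attachment 9.2, by number of terms: gallbladder and biliary 62, liver safety 23, coagulation 15, pancreatitis 15, low blood cell 11. The protocol side comes from 3.5.2.8, Table 3-1 with its footnotes, and 6.5.2.

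| Item in the protocol | Category for that risk | Terms found there | Terms found elsewhere |
|---|---|---|---|
| Alkaline phosphatase | Liver safety | 0 | 2, gallbladder/biliary |
| Bilirubin, any term | Liver safety | 1 (*Urine bilirubin increased*) | 10, gallbladder/biliary, including the same urine term |
| Jaundice | Liver safety | 0 | 3, gallbladder/biliary |
| Amylase | Pancreatitis | 0 | 0 |
| APTT | Coagulation | 0 | 0 |
| Neutrophils | Low blood cell | 2 (*Neutropenia*, *Febrile neutropenia*); no count-decreased term | 0 |
| White cells | Low blood cell | 1 (*Leukopenia*); no count-decreased term | 0 |

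**Liver.** Of the five tests in the protocol's liver group, ALT, AST and γGT each have an increased and an abnormal term in liver safety. Alkaline phosphatase and total bilirubin have no blood-test term there: 5 − 3 = 2 of 5. *Hyperbilirubinaemia* and *Hepatitis cholestatic* are also under gallbladder and biliary only.

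**Is the split a rule against overlap?** No. *Urine bilirubin increased* is in both the gallbladder/biliary and liver lists. *Electrocardiogram QT prolonged* and *Long QT syndrome* are in both the bradycardia and QT lists. The attachment already allows shared terms.

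**Pancreatitis.** The list has trypsin, lipase and general pancreatic-enzyme terms. Amylase, the only pancreatic enzyme that the protocol names for collection, has none.

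**Coagulation.** The protocol collects prothrombin time and APTT. The list has prothrombin-time and thrombin-time terms and two *Blood thromboplastin* terms (abnormal, decreased), but none for APTT.

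**Low blood cell.** The list pairs *Lymphopenia* with *Lymphocyte count decreased*, and *Thrombocytopenia* with *Platelet count decreased*. *Neutropenia* and *Leukopenia* have no such partner, although Table 3-1 lists both neutrophils and WBC.

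**Size.** For one category, let *a* be the patients with at least one event on the list, and *b* those whose only relevant events are coded to terms not on it. The table shows *a*, the complete count is *a* + *b*, and the relative shortfall is *b*/(*a* + *b*). The documents give neither *a* nor *b*, so no figure follows.

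**The case against.** The case on the other side has weight.

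- The category is gallbladder *and biliary*. Alkaline phosphatase, bilirubin, jaundice and cholestasis form a sensible biliary group, and SAP 8.4.1 allows project-defined groups of similar events. The named risk is increased liver enzymes, and bilirubin is not an enzyme. Table 3-1 places total bilirubin under blood chemistry, and the jaundice sentence is a clinical-management statement. This stands as a reason to keep the terms where they are. It is not a reason to leave them out of liver safety, since both documents put alkaline phosphatase and total bilirubin in the liver group.
- General terms such as *Hepatic enzyme increased*, *Liver function test increased* and *Pancreatic enzymes increased* may catch some events. A patient with another event in the category is counted anyway. This stands: an undercount is possible, not certain.
- All treatment-emergent events are tabulated by system organ class and preferred term, and laboratory data have shift tables and listings (SAP 8.4.1, 8.4.2). This stands, so the signals are not lost. But counts by preferred term cannot be added into patients per risk category, and the shift tables do not show relationship, seriousness or action taken.
- The list may be updated before lock. That is the route for the correction; it does not supply the content.

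A reader might infer more than the documents support. Low neutrophil and white-cell events do have terms (*Neutropenia*, *Febrile neutropenia*, *Leukopenia*). The liver terms are not dropped from the AESI tables, but appear as rows under gallbladder and biliary. The coagulation list has *International normalised ratio abnormal* without an increased form, but INR is not among the protocol's laboratory parameters, so that is not a mismatch with the protocol.

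**Conclusion.** The point holds as a possible undercount in four AESI categories: liver, pancreatitis, coagulation and low blood cells. Two kinds of effect should be kept apart. Alkaline phosphatase, blood bilirubin, jaundice and cholestatic hepatitis events stay in the AESI tables but join the gallbladder and biliary subtotal alone. Events coded to specific amylase, APTT, neutrophil-count or white-cell-count terms would fall outside the AESI tables.

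The conclusion assumes that the printed list is applied as it stands and that some events are coded to those terms. How site wording would be coded depends on MedDRA, which the documents do not reproduce. The structural size is 2 of 5 liver tests without a blood-test term in liver safety. A percentage undercount would rest on invented event rates, so none is given. It would also be wrong to infer that the primary endpoint is affected: it counts pasireotide-related adverse events and serious adverse events and does not use the AESI list.

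The change is still worth making. Patient counts per named risk are a planned output of a safety study, no other table supplies them, and the correction is cheap.

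**What to change.** Before database lock, amend Attachment 9.2 as follows.

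- **Liver safety:** add the alkaline phosphatase, blood bilirubin, hyperbilirubinaemia, jaundice and cholestatic hepatitis terms. Keep them under gallbladder and biliary too, and footnote the shared terms.
- **Pancreatitis:** add amylase increased and amylase abnormal.
- **Coagulation:** add APTT prolonged.
- **Low blood cell:** add neutrophil count decreased and white-cell count decreased.
- **All categories:** check each list against the laboratory parameters in protocol 3.5.2.8 and Table 3-1. Take the exact term names from the MedDRA version used for coding.

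The cost is a list edit and a rerun of the AESI tables. Shared terms will count in two categories, so category totals must not be added together; the footnote should say so.
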